4.2. Statistical Hypotheses

Part 1

The primary study objective on immune response in Part 1 is based on the participants who will receive the 4th dose in Part 1 of the study.

Primary Hypotheses:

- 1) mRNA-1273.529, as a single booster dose, is non-inferior to mRNA-1273 based on GMR against the B.1.1.529 strain with a non-inferiority margin of 1.5 at Day 29.
- 2) mRNA-1273.529, as a single booster dose, is non-inferior to mRNA-1273 based on GMR against the B.1.1.529 strain with a non-inferiority margin of 1.5 at Month 3.

Key Secondary Hypothesis:

mRNA-1273.529, as a single booster dose, is superior to mRNA-1273 based on GMR against the B.1.1.529 strain at Day 29 or Month 3.

For the primary objective of immune response, hypotheses testing based on participants receiving the 4th dose, alpha of 0.05 (two-sided) will be allocated between the two time points. Alpha of 0.01 (two-sided) will be allocated to Day 29 and alpha of 0.04 (two-sided) will be allocated to Month 3.

The non-inferiority of mRNA-1273.529 as compared to mRNA-1273 against the B.1.1.529 strain at Day 29 will be assessed using a non-inferiority margin of 1.5 at two-sided alpha of 0.01. The primary immunogenicity objective is considered met if non-inferiority against the

B.1.1.529 strain is demonstrated, i.e., the lower bound of the 99% confidence interval (CI) of the GMR of mRNA-1273.529 vs. mRNA-1273 against B.1.1.529 is ≥ 0.67 (1/1.5).

The non-inferiority of mRNA-1273.529 as compared to mRNA-1273 against the B.1.1.529 strain at Month 3 will be assessed using a non-inferiority margin of 1.5 at two-sided alpha of 0.04. The primary immunogenicity objective is considered met if non-inferiority against the B.1.1.529 strain is demonstrated, i.e., the lower bound of the 96% confidence interval (CI) of the GMR of mRNA-1273.529 vs. mRNA-1273 against B.1.1.529 is ≥ 0.67 (1/1.5).

Part 2

The primary objective on immune response in Part 2 is based on the participants who will receive the 4th dose in Part 2 of the study. There are six hypotheses on immune response of mRNA-1273.214 listed below. Part 2 of this study is considered to have met its primary objective if non-inferiority of mRNA-1273.214 against the B.1.1.529 strain, non-inferiority of mRNA-1273.214 against the prototype strain, and superiority of mRNA-1273.214 against the B.1.1.529 strain are demonstrated as compared to mRNA-1273 at Day 29 or Month 3.

Figure 2 details the hypotheses testing strategy specific to Part 2.

Primary Hypotheses:

- 1) mRNA-1273.214, as a single booster dose, is non-inferior to mRNA-1273 based on GMR against the B.1.1.529 strain with a non-inferiority margin of 1.5 at Day 29.
- 2) mRNA-1273.214, as a single booster dose, is non-inferior to mRNA-1273 based on GMR against the prototype strain with a non-inferiority margin of 1.5 at Day 29.
- 3) mRNA-1273.214, as a single booster dose, is superior to mRNA-1273 based on GMR against the B.1.1.529 strain at Day 29.
- 4) mRNA-1273.214, as a single booster dose, is non-inferior to mRNA-1273 based on GMR against the B.1.1.529 strain with a non-inferiority margin of 1.5 at Month 3.
- 5) mRNA 1273.214, as a single booster dose, is non-inferior to mRNA -1273 based on GMR against the prototype strain with a non-inferiority margin of 1.5 at Month 3.
- 6) mRNA-1273.214, as a single booster dose, is superior to mRNA-1273 based on GMR against the B.1.1.529 strain at Month 3.

For the primary objective of immune response, hypotheses testing based on participants receiving the 4th dose, alpha of 0.05 (two-sided) will be allocated to the two time points: alpha of 0.01 (two-sided) will be allocated to Day 29, and alpha of 0.04 (two-sided) will be allocated to Month 3.

[figure not shown]
For the primary immunogenicity objective, the non-inferiority of mRNA-1273.214 as compared to mRNA-1273 against the B.1.1.529 strain and the non-inferiority of mRNA-1273.214 as compared to mRNA-1273 against the prototype strain at Day 29 will be assessed using a non-inferiority margin of 1.5 at two-sided alpha of 0.01. The primary immunogenicity objective is considered met if non-inferiority against the B.1.1.529 strain and the prototype strain are both demonstrated, i.e., the lower bound of the 99% confidence interval (CI) of the GMR of mRNA-1273.214 vs. mRNA-1273 against B.1.1.529 is ≥ 0.67 (1/1.5) and the lower bound of the 99% CI of the GMR of mRNA-1273.214 vs mRNA-1273 against prototype is ≥ 0.67 .

Superiority of mRNA-1273.214 as compared to mRNA-1273 against the B.1.1.529 strain will be evaluated at Day 29. Once the non-inferiority of mRNA-1273.214 as compared to mRNA-1273 against the B.1.1.529 strain and against the prototype strain is demonstrated, the 99% CI of GMR (mRNA-1273.214 vs. mRNA-1273) will be used to assess superiority

of mRNA-1273.214 as compared to mRNA-1273. If the lower bound of the GMR rules out (> 1) at Day 29, superiority of mRNA-1273.214 compared to mRNA-1273 against B.1.1.529 will be considered demonstrated.

Hypotheses testing at Month 3 will be performed in the same manner, first testing two non-inferiority hypotheses (one against the B.1.1.529 strain and one against the prototype strain) at alpha of 0.04 level (two-sided). Once non-inferiority is demonstrated for both B.1.1.529 and prototype strains, then superiority testing against the B.1.1.529 at alpha of 0.04 level (two-sided) will be performed.

Figure 2 Statistical hypothesis testing strategy of mRNA-1273.214 vs. mRNA-1273 (Part 2)

Abbreviations: M = month; mRNA = messenger ribonucleic acid.

4.3. Sample Size and Power

Two groups of participants will be included in this study:

1. Participants who received two doses of a COVID-19 vaccine as the primary series and the 3rd dose of a COVID-19 vaccine and will receive the 4th dose as part of the study.
2. Participants who received two doses of a COVID-19 vaccine as the primary series and will receive the 3rd dose as part of the study.

Part 1 (50 µg mRNA-1273.529 and 50 µg mRNA-1273 in 1:1 ratio)

The primary immunogenicity objective is to assess immune response of mRNA-1273.529 against B.1.1.529 strain in participants who are receiving mRNA-1273.529 (or mRNA-1273) as the 4th dose in Part 1 of this study.

The target enrollment is approximately 500 participants (minimum 300 participants) in each treatment arm (1:1). The assumptions are: 1) at least **CCI** participants will be in 4th dose subgroup; and 2) **CCI** of participants will be excluded from the Per-Protocol (PP) Set for immunogenicity, SARS-CoV-2 negative (e.g., due to infection with the SARS-CoV-2 Omicron variant).

Statistical power for hypotheses testing at Day 29 (alpha=0.01, two-sided):

With approximately **CCI** evaluable participants per arm, there is **CCI** power to demonstrate non-inferiority of mRNA-1273.529 against the B.1.1.529 strain at two-sided alpha of 1.0% at Day 29. With this range of sample sizes, the power to demonstrate superiority of mRNA-1273.529 against the B.1.1.529 variant strain at a two-sided alpha of 1% at Day 29 ranges from **CCI**. The assumptions are: the true GMR (mRNA-1273.529 vs mRNA-1273) ranges from **CCI**, the standard deviation of the natural log-transformed titer is **CCI**, with a non-inferiority margin of 1.5.

Statistical power for hypotheses testing at Month 3 (alpha=0.04, two-sided):

With approximately **CCI** evaluable participants per arm, there is **CCI** power to demonstrate non-inferiority of mRNA-1273.529 against the B.1.1.529 strain at two-sided alpha of 4% at Month 3. With this range of sample sizes, the power to demonstrate superiority of mRNA-1273.529 against the B.1.1.529 variant strain at a two-sided alpha of 4% at Month 3 ranges from **CCI**. The assumptions are: the true GMR (mRNA-1273.529 vs mRNA-1273) ranges from **CCI**, the standard deviation of the natural log-transformed titer is **CCI**, with a non-inferiority margin of 1.5. Specific operating characteristics for Part 1 are provided in [Table 3](#). With approximately **CCI** participants receiving the 4th dose in each study arm, there is at least 90% probability to observe one participant reporting an AE in each study arm if the true incidence of AEs is 1%.

Table 3 Operating Characteristics and Power for the Primary and Key Secondary Objectives Under Various GMRs and the Number of Evaluable Participants with Immunogenicity Data Who Receives the 4th Dose in this Study (Part 1)

True GMR (mRNA-1273.529 vs. mRNA-1273 against B.1.1.529)	Number evaluable patients per arm (4 th dose)	Minimum empirical GMR for the primary objective	Power
Two-sided Type I Error (α) = 0.01 (Day 29)			
Primary Objective: Non-inferiority (lower bound of the $(1-\alpha) * 100\%$ of GMR ≥ 0.67)			
			
Key Secondary Objective: Superiority (lower bound of the $(1-\alpha) * 100\%$ of GMR rules out 1)			
			
Two-sided Type I Error (α) = 0.04 (Month 3)			
Primary Objective: Non-inferiority (lower bound of the $(1-\alpha) * 100\%$ of GMR ≥ 0.67)			
			
Key Secondary Objective: Superiority (lower bound of the $(1-\alpha) * 100\%$ of GMR rules out 1)			
			

Abbreviations: GMR = geometric mean titer ratio; mRNA = messenger ribonucleic acid.

Part 2 (50 µg mRNA-1273.214 and 50 µg mRNA-1273 in 1:1 ratio)

The primary immunogenicity objective is to assess immune response of mRNA-1273.214 against B.1.1.529 and prototype in participants who are receiving mRNA-1273.214 (or mRNA-1273) as the 4th dose in Part 2 of this study. The sample size is driven by this subgroup.

Hypotheses testing on immunogenicity data will be performed at two time points: Day 29, and Month 3 post-booster. To preserve family-wise alpha of 0.05 (two-sided), alpha will be allocated to Day 29 of 0.01 (two-sided), and Month 3 of 0.04 (two-sided).

Statistical power for hypotheses testing at Day 29 (alpha=0.01, two-sided):

For the 4th dose subgroup, the target enrollment is approximately 1328 participants in each treatment arm (1:1). Assuming CCI of participants will be excluded from the PP Set for Immunogenicity, SARS-CoV-2 negative, with approximately CCI evaluable participants in each arm, there is CCI power to demonstrate non-inferiority of mRNA-1273.214 against the B.1.1.529 and against the prototype at two-sided alpha of 1.0%. With this sample size, there is approximately CCI power to demonstrate superiority of mRNA-1273.214 against the B.1.1.529 variant strain at a two-sided alpha of 1.0% at Day 29. The assumptions are: the true GMR (mRNA-1273.214 vs. mRNA-1273) against the B.1.1.529 strain ranges from CCI and the true GMR (mRNA-1273.214 vs. mRNA-1273) against the prototype strain is CCI, the standard deviation of the natural log-transformed titer is CCI, with a non-inferiority margin of 1.5.

Statistical power for hypotheses testing at Month 3 (alpha=0.04, two-sided):

With approximately CCI evaluable participants in each arm, there is CCI power to demonstrate non-inferiority of mRNA-1273.214 against the B.1.1.529 and against prototype at two-sided alpha of 4%. With this sample size, there is approximately CCI power to demonstrate superiority of mRNA-1273.214 against the B.1.1.529 strain at a two-sided alpha of 4% at Month 3. The assumptions are: the true GMR (mRNA-1273.214

vs. mRNA-1273) against the B.1.1.529 strain ranges from CCI and the true GMR (mRNA-1273.214 vs. mRNA-1273) against the prototype strain is CCI, the standard deviation of the natural log-transformed titer is CCI, with a non-inferiority margin of 1.5.

[figure not shown]
With approximately 1328 participants receiving the 4th dose in each study arm, there is at least 90% probability to observe one participant reporting an AE in each study arm if the true incidence of AEs is 1%.

The enrollment target of this study is approximately 1328 participants per arm to receive the 4th dose. The Omicron variant of concern (VOC) has spread quickly throughout the world. There may be an urgency to perform Day 29 or Month 3 analysis as early as possible, and depending on the operational feasibility, particularly the testing capability of assays of antibodies against B.1.1.529, the Sponsor may decide to perform the analysis of immunogenicity after immunogenicity data from a subset of the participants receiving the 4th dose becomes available. Such a decision will be documented prior to the planned analysis at Day 29 or Month 3.

Table 4 includes the power and operating characteristics under various GMRs and two different scenarios for the number of evaluable participants with immunogenicity data. Based on CCI evaluable participants per arm (4th dose), under the same assumptions outlined above, there is CCI power to demonstrate non-inferiority of mRNA-1273.214 compared to mRNA-1273 against B.1.1.529 at Day 29 at $\alpha = 1\%$ if true GMR CCI; and there is approximately CCI power to demonstrate superiority at $\alpha = 1\%$ if the true ratio is CCI. With this size, there is CCI power at Month 3 (primary objective) at $\alpha = 4\%$ (two-sided) if the true GMR is CCI and there is CCI power to demonstrate superiority at $\alpha = 4\%$ (two-sided) if the true GMR is CCI.

Table 4 Operating Characteristics and Power for the Primary and Key Secondary Objectives Under Various GMR and the Number of Evaluable Participants with Immunogenicity Data Who Receives the 4th Dose in this Study (Part 2)

True GMR (mRNA-1273.214 vs. mRNA-1273 against B.1.1.529)	Number evaluable patients per arm (4 th dose)	Minimum empirical GMR for the primary objective	Power
Two-sided Type I Error (α) = 0.01 (Day 29)			
Primary Objective: Non-inferiority (lower bound of the $(1-\alpha) * 100\%$ of GMR ≥ 0.67)			
CCI			

Abbreviations: GMR = geometric mean titer ratio; mRNA = messenger ribonucleic acid.

4.4. Multiplicity

Statistical testing in Part 1 is independent of testing in Part 2. In each Part, the family-wise alpha of 0.05 (two-sided) will be preserved by allocating alpha across two time points: 0.01 (two-sided) at Day 29 and 0.04 (two-sided) at Month 3.

4.5. Randomization

Randomization will be performed using an interactive response technology (IRT). In Part 1, approximately 600-1000 participants will be randomized in a 1:1 ratio to receive a single dose of either 50 µg of mRNA-1273.529 or 50 µg of mRNA-1273 (active control). In Part 2, approximately 2,924 participants will be randomized in a 1:1 ratio to receive a single dose of either 50 µg of mRNA-1273.214 or 50 µg of mRNA-1273 (active control). In both parts, randomization will be stratified by age groups (16 to < 65 years or ≥ 65 years) and number of booster doses received (to receive study vaccine as the 4th dose or to receive study vaccine as the 3rd dose). At least 90% of participants will receive study vaccine as the 4th dose. There will be four randomization strata for each part:

- ≥ 16 and < 65 years, receive IP as a 4th dose
- ≥ 65 years, receive IP as a 4th dose
- ≥ 16 and < 65 years, receive IP as a 3rd dose
- ≥ 65 years, receive IP as a 3rd dose

4.6. Blinding and Unblinding

As the appearance of the study vaccines differs, enrollment will be observer-blinded as to treatment assignment.

The investigator, clinic staff, study participants, site monitors, and Sponsor personnel (or its designees) will be blinded to the IP administered until the study database is locked and unblinded for the final analysis. Once participants become eligible to obtain an additional booster outside of the study, they become eligible for optional unblinding and continue in Phase B of the study part they were enrolled. In Part 1, participants in either treatment arm are eligible to choose to be unblinded to study treatment after completion of the Month 6 visit. In Part 2, participants in either treatment arm are eligible to choose to be unblinded to study treatment after completion of the Month 3 visit. If a participant decides to obtain an additional booster, the booster would be obtained outside the study. Additionally, participants can choose to not be unblinded after completion of the Month 6 (Part 1) and Month 3 (Part 2) visits. All participants are encouraged to continue the study regardless of choosing to be unblinded or remain blinded and/or choosing to obtain an additional booster external to the study. The optional unblinding will be performed at the participant level by a study site member via the IRT system with all other site members remaining blinded to original treatment assignment.

At the planned analysis (see [Section 6.6](#)), pre-identified Sponsor team members and selected contract research organization (CRO) team members will be unblinded to conduct the analyses. Study participants, investigators, and blinded site personnel will remain blinded.

Planned primary analysis are described in [Section 6.6](#) of this SAP and Section 9.7 of the protocol. Participant-level unblinding will be restricted to an independent unblinded statistician and as needed, statistical programmer(s) performing the primary analysis, who will have no other responsibilities associated with the study.

An independent unblinded statistical and programming team who are not involved in study design and conduct of the CRO will perform the planned primary analysis ([Section 6.6.1](#)). Select Sponsor team members including biostatistician and statistical programmers will be prespecified to be unblinded to the primary analysis results and will not communicate the results to the blinded investigators, clinic staff, clinical monitors, or participants. The details will be included in the Study Blinding Plan.

In addition to the routine study monitoring outlined in this protocol, an external DSMB will review interim safety data to safeguard the interests of clinical study participants and to enhance the integrity of the study. The DSMB will review treatment-level safety data, provided by the independent unblinded statistician. Limited additional Sponsor personnel may be unblinded to the treatment-level results of the safety analyses, if required, to act on the recommendations of the DSMB.

The extent to which individuals are unblinded with respect to results of primary and safety analyses will be documented. The limited Sponsor and CRO team members to be unblinded in this case will be pre-specified in the study Data Blinding Plan. Participants and investigators will remain blinded until the unblinding or participant decision visit.

5. Analysis Populations

The following analysis sets are defined for each part: Randomized Set, Full Analysis Set (FAS), Modified Intent-to-Treat (mITT), PP Set for Immunogenicity (PPSI), PP Set for Immunogenicity – SARS-CoV-2 negative (PPSI-Neg), Solicited Safety Set, Safety Set, and PP Set for Efficacy (PPSE).

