4. STUDY DESIGN

4.1. General Design

The study is a Phase 2/3, 2-part, randomized, observer-blind, active-controlled, multicenter study to evaluate the immunogenicity and safety of mRNA-1273.529 and mRNA-1273.214 booster vaccine in medically stable individuals 16 years and older. The mRNA-1273.529 vaccine to be tested in this study contain mRNAs encoding for the S-2P of the SARS-CoV-2 Omicron variant (B.1.1.529). The mRNA-1273.214 vaccine contains the Wuhan Hu-1 and B.1.1.529 mRNAs (2 mRNAs: CX024414 encoding for the S-2P of Wuhan Hu-1 and CX-031302 encoding for the S-2P of B.1.1.529) and formulated in the same LNP.

The study consists of 2 parts with 2 phases each:

In **Part 1**, approximately 600-1000 participants will be randomized in a 1:1 ratio to 1 of 2 study arms to receive a single dose of either 50 μ g of mRNA-1273.529 or 50 μ g of mRNA-1273 (active control). Randomization will be stratified by age groups (16 to < 65 years or \geq 65 years) and number of booster doses received (to receive study vaccine as the 4th dose or to receive study vaccine as the 3rd dose). At least \geq 90% of participants will receive study vaccine as the 4th dose. The potential number of participants in each arm and the randomization ratio can be found in [Table 5](#).

In **Part 2**, approximately 2,924 participants will be randomized in a 1:1 ratio to 1 of 2 study arms to receive a single dose of either 50 μ g of mRNA-1273.214 or 50 μ g of mRNA-1273 (active control). Randomization will be stratified by age groups (16 to < 65 years or \geq 65 years) and number of booster doses received (to receive study vaccine as the 4th dose or to receive study vaccine as the 3rd dose). At least \geq 90% of participants will receive study vaccine as the 4th dose. The potential number of participants in each arm and the randomization ratio can be found in [Table 6](#).

Each part has a Phase A (randomized, blinded) and Phase B (open-label, observational). Phase B was designed to offer eligible participants in either treatment arms in Part 1 to obtain an additional booster after their Month 6 assessment and eligible participants in either treatment arms in Part 2 the option to obtain an additional booster after their Month 3 assessment. The additional booster may be obtained outside the study.

Table 5: Part 1 Study Arm and Dose Levels

Vaccination Group	Vaccination Received	Total Dose	N (total)	Study vaccine as the 3 rd dose	Study vaccine as the 4 th dose

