Except in the case of medical necessity and optional unblinding ([Section 6.3.7](#)), a participant's treatment should not be unblinded without the approval of the Sponsor. The treatment code should be broken only if the investigator in charge of the participant feels that the case cannot be treated without knowing the identity of the study vaccine. Instructions regarding emergency unblinding will be provided to the investigator and are discussed in [Section 6.3.7](#).

The investigator, clinic staff, study participants, site monitors, and Sponsor personnel (or its designees) will be blinded to the IP administered until the unblinding occurs ([Section 6.3.7](#)) or until study database is locked and unblinded for the final analysis. At the planned analyses (see [Section 9.7](#)), pre-identified Sponsor team members and selected contract research organization (CRO) team members will be unblinded to conduct the analyses.

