6.3.7. Unblinding

Participants who report eligibility to receive an additional booster outside of the mRNA-1273-P305 study have the option to be unblinded in Part 1 of the study after the completion of their scheduled Month 6 visit and in Part 2 after the completion of their scheduled Month 3 visit.

Unblinding may be performed remotely over the phone prior to signing the updated informed consent form (ICF) based on participant preference. Both unblinded and blinded participants will continue to follow the Schedule of Events ([Section 1.3](#)).

Except in the case of medical necessity and as part of the unblinding described above, a participant's treatment assignment should not be unblinded without the approval of the Sponsor. If a participant becomes seriously ill or pregnant during the study, the blind will be broken only if knowledge of the treatment assignment will affect that participant's clinical management. The investigator will be responsible for documenting the time, date, reason for unblinding, and the names of the personnel involved. The investigator (or designee) will have access to unblind participants within IRT. All unblindings will be tracked via an audit trail in IRT and documented in the final study report.

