9.1. Blinding and Responsibility for Analyses

Phase A of this study is observer-blind. The study participants, investigators, site personnel, site monitors, and Sponsor personnel (or its designees) will be blinded to the IP administered until the unblinding occurs ([Section 6.3.7](#)) or until study database is locked and unblinded, with the following exceptions:

- An independent unblinded statistical and programming team who are not involved in study design and conduct of the CRO will perform the planned primary analysis, ([Section 9.7](#)). Select Sponsor team members including biostatistician and statistical programmers will be prespecified to be unblinded to the primary analysis results and will not communicate the results to the blinded investigators, clinic staff, clinical monitors, or participants. The details will be included in the Data Blinding Plan.
- The DSMB may review data, as appropriate, to safeguard the interests of clinical study participants and to help ensure the integrity of the study.

Procedures for breaking the blind in the case of a medical necessity are provided in [Section 6.3.7](#).

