3.1.2. Primary Safety Endpoints

The primary safety objectives will be evaluated by the following endpoints in Part 1 and Part 2:

- Solicited local and systemic reactogenicity adverse reactions (ARs) during a 7-day follow-up period after vaccination.
- Unsolicited adverse events (AEs) through the 28-day follow-up period after vaccination.

- Serious AEs (SAEs), medically attended AEs (MAAEs), AEs leading to withdrawal, and AEs of special interest (AESIs) from Day 1 to end of study.

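### SAP 4.6 contradicts itself, and in part the protocol, on whether investigators stay blinded after a participant's optional unblinding, so late severity and relatedness ratings could be made knowing the arm

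*SAP*

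**What the plan says.** SAP 4.6 makes three statements about the site's blind.

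- The second paragraph opens with the investigator, clinic staff and participants, among others, who "will be blinded to the IP administered until the study database is locked and unblinded for the final analysis".
- The same paragraph ends by saying that optional unblinding is done per participant "by a study site member via the IRT system with all other site members remaining blinded to original treatment assignment".
- The last sentence of the section reads: "Participants and investigators will remain blinded until the unblinding or participant decision visit".

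The protocol has its own version. Section 6.2 says that the investigator and clinic staff, among others, "will be blinded to the IP administered until the unblinding occurs", with a pointer to 6.3.7, or until lock for the final analysis. Section 9.1 says the same for Phase A: "The study participants, investigators, site personnel, site monitors, and Sponsor personnel (or its designees) will be blinded to the IP administered until the unblinding occurs". On who carries it out, 6.3.7 adds: "The investigator (or designee) will have access to unblind participants within IRT". The protocol nowhere limits knowledge of the assignment to one site member.

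The late safety outcomes are primary endpoints in SAP 3.1.2: "Serious AEs (SAEs), medically attended AEs (MAAEs), AEs leading to withdrawal, and AEs of special interest (AESIs) from Day 1 to end of study". Protocol 8.10.9 has the investigator judge causality for all AEs and SAEs. Protocol 8.10.8 has the investigator judge severity of unsolicited AEs.

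**The concern.** A site cannot tell from these texts whether the person who rates adverse events should still be blinded after a participant opts to be unblinded. If that person may know the arm, or even looks it up, then severity and relatedness of later events become open-label judgements in a comparison of a new vaccine with mRNA-1273. The SAP uses those judgements beyond the unblinding point. Under SAP 6.3.1, unsolicited AEs are summarised both to 28 days and throughout the study. The overall summary in 6.3.1.1 gives severe events, and treatment-related counts within each category. SAP 6.3.1.2 tabulates severe events by SOC and PT throughout the study.

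The loss is avoidable. Phase B exists so that participants can obtain a booster outside the study (protocol 4.1 and 4.2). That purpose needs the participant, not the assessor, to know the assignment. Protocol 6.2 already provides unblinded site staff who take no part in participant evaluations.

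**Working it through.** The plan states no figure on this point, so the main check is a comparison of texts.

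**Does the investigator stay blinded after optional unblinding?** Under the opening sentence of the second paragraph of SAP 4.6, yes, until final lock. That sentence also keeps participants blinded until final lock, which the rest of its own paragraph contradicts. Under the closing sentence of that paragraph, yes, unless the investigator is the one member who unblinds. Under the last sentence of SAP 4.6 and protocol 6.2 and 9.1, no.

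**Who may do it?** The SAP says a site member and does not exclude an AE assessor. Protocol 6.3.7 names the investigator or a designee. Even the stricter SAP sentence therefore does not by itself keep the assessor blinded.

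**When does the blind end?** The *participant decision visit* is defined in neither document and is absent from both Schedules of Events. Read literally, it could end the investigator's blind even for a participant who decides to stay blinded.

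**Does precedence settle it?** The SAP Introduction says that the SAP prevails over the protocol. That cannot help where the SAP disagrees with itself. SAP 7 declares no change from the protocol.

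**Which outcomes are reached?** Optional unblinding follows the Month 6 visit in Part 1 and the Month 3 visit in Part 2 (protocol 6.3.7). Solicited reactions (7 days), unsolicited AEs (28 days) and the Day 29 and Month 3 titres are all collected before it. Only the Day 1 to end-of-study safety events run past it.

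**How much follow-up?** Inputs are the visit days and windows in the Schedules of Events: Month 3 = Day 85 (±7), Month 6 = Day 179 (±14), Month 12 = Day 359, which is 358 days after vaccination. Share = (359 − visit day)/358.

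- Part 2: (359 − 85)/358 = 274/358 = 76.5%. Across the visit window: 267/358 = 74.6% to 281/358 = 78.5%.
- Part 1: (359 − 179)/358 = 180/358 = 50.3%. Across the visit window: 166/358 = 46.4% to 194/358 = 54.2%.

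These are maxima for one participant who unblinds at the earliest visit.

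**How far does the calendar reduce this?** Optional unblinding came with Amendment 2, dated 26 August 2022 (SAP Introduction). The other inputs are the synopsis estimates, 07 Feb 2022 for first enrolment and 07 Apr 2023 for last completion, and the Amendment 1 date, 03 Mar 2022.

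- Last participant: 07 Apr 2023 − 358 days = 14 Apr 2022. From then to 26 Aug 2022 is 134 days, leaving 358 − 134 = 224 days, and 224/358 = 62.6%.
- Dosed 03 Mar 2022: 176 days elapsed, 182 left, 182/358 = 50.8%. This is an early Part 2 case, since Amendment 1 introduced Part 2.
- First Part 1 participant, dosed 07 Feb 2022: 200 days elapsed, 158 left, 158/358 = 44.1%. A Part 1 participant dosed on 03 Mar 2022 reaches Month 6 (178 days) just after the amendment date, so the nominal 180/358 remains possible.

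Sites could act only after ethics approval of the amendment (protocol 11.1.7), so the real shares are lower still.

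**The case against.** The strongest reply is that Phase B is open by declaration: "Each part has a Phase A (randomized, blinded) and Phase B (open-label, observational". Protocol 9.1 limits the observer blind to Phase A, and protocol 9.7 and SAP 6.6 call the Month 6, Month 12 and Phase B analyses exploratory. On this view protocol 6.2, 6.3.7 and 9.1 agree with each other, and only the SAP wording needs tidying.

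Much of the detail behind this reply stands.

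- A reader might infer that the late primary safety endpoints themselves are biased. The documents do not support that. The endpoints are occurrences: an MAAE is defined by an unscheduled visit to a healthcare practitioner (protocol 8.10.4), AESIs by a list of medical concepts (11.3), SAEs mainly by outcome (8.10.2). Protocol 8.10.9 says that the causality rating does not decide what is reported.
- SAP 6.1 makes the first 28 days the primary period for safety analyses, and the treatment-related SOC/PT tables in 6.3.1.2 stop there. Late relatedness enters mainly through the overall summary. That summary is descriptive, and protocol Table 12 plans no confidence intervals for it.
- Suspected myocarditis, pericarditis and myopericarditis go to a blinded committee (protocol 8.11), but no other events do.
- Delegation is already allowed, and a participant may tell the investigator anyway.

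The open-label label does not dispose of the point. The Day 1 to end-of-study events remain listed as primary, they are summarised throughout the study, and the SAP sentence restricting knowledge to one site member shows that the authors meant to protect site staff.

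**Conclusion.** The contradiction is established from the text. Its consequence is a possibility: for participants who choose unblinding, investigator ratings of severity and relatedness of later SAEs, MAAEs, AESIs and AEs leading to withdrawal could be made knowing the arm. This could bias the descriptive throughout-study severe and treatment-related counts. The primary immunogenicity result is untouched.

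Two stronger readings should be resisted. The first is that 77% (Part 2) or 50% (Part 1) of safety follow-up is open-label. Those are per-participant maxima, uptake is not stated, and on the estimated dates Part 2 stays near or below 63%. The second is a numerical bias. Suppose 10% of the 1462 per arm have a late MAAE, and knowledge of the arm moves the related share from 2% to 4% in the new-vaccine arm only. Related events would be 1462 × 0.10 × 0.02 = 2.9 with no uptake, 73.1 × 0.02 + 73.1 × 0.04 = 4.4 at half uptake, and 1462 × 0.10 × 0.04 = 5.8 at full uptake. Every rate there is assumed, so this shows only that the size depends on unknowns.

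The change is worth making because the remedy is cheap and uses roles the protocol already has.

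**What to change.** State one rule in SAP 4.6 (the opening and closing sentences of the second paragraph, and the last sentence of the section) and in protocol 6.2, 6.3.7 and 9.1:

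- Optional unblinding is carried out by the already unblinded pharmacy or vaccine-administration staff, never by anyone who assesses AEs or COVID-19 cases.
- Those assessors, including the investigator, stay blinded after a participant's optional unblinding.
- Investigator access in IRT is kept for the medical-necessity unblinding that the protocol already allows.

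Add the task to the unblinded staff's duties in protocol 6.2. That section now limits them to product handling, bars them from revealing the product to participants except in an emergency, and leaves all contact after injection to blinded staff. It needs an exception for this one task. Define *participant decision visit* or delete it.

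Where unblinding has already happened, report end-of-study safety events by arm, split by before and after participant-level unblinding, with person-time and the number unblinded. The IRT audit trail in protocol 6.3.7 supplies the dates. In SAP 6.1 change *may* to *will* for this. The subsets listed there classify participants, so the split of events by date must be added. Because participants choose unblinding, the split is descriptive.

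The cost is wording in two documents, an IRT role setting, one small added task for unblinded staff and one extra table. Protection is partial: a participant may disclose the arm, and ratings already made by an unblinded investigator cannot be undone, only shown separately.
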